### 6.9.1 Prohibited Medications

The following treatments are prohibited for all participants during the Treatment Period:

- Any biologic or small molecule immunosuppressive therapy that would have potential therapeutic impact on the disease being studied, including but not limited to anti-TNF (eg, adalimumab, certolizumab pegol, etanercept, golimumab, infliximab, etc), anti-IL1 (eg, anakinra, canakinumab, bermekimab), anti-IL12/23 (eg, ustekinumab), other anti-IL23 (eg, guselkumab), anti-IL-17 (eg, secukinumab, bimekizumab), JAK inhibitors, or TYK inhibitors.
- Any other systemic therapy that can also be used to treat HS, including but not limited to apremilast, corticosteroids, methotrexate, cyclosporine, retinoids, acitretin/etretinate, hormonal therapy (except for contraception), zinc gluconate, intramuscular gamma-globulin, colchicine, metformin (except for continuous treatment of pre-existing diabetes), and fumaric acid esters.
- Any antibiotic therapy (topical and/or systemic [oral or IV]) for HS-related infection.  
Exception:
  - Participants who have been on a stable dose and frequency of a permitted oral antibiotic therapy (doxycycline up to 100 mg PO BID or minocycline up to 100 mg PO BID) for at least 4 consecutive weeks (28 days) prior to Baseline and throughout the duration of the 28-week Treatment Period of the trial. Additionally, systemic and/or topical antibiotic use is allowed for the treatment of acute, non-HS-related infections.
  - Participants who receive antibiotic therapy for HS-related infections will not be randomized if they start oral antibiotic therapy or increase dose of concomitant oral antibiotic therapy within 28 days of Baseline and will be counted as a non-responder and meet criteria for permanent discontinuation if they start oral antibiotic therapy or increase the dose of concomitant oral antibiotic therapy during the Treatment Period. Participants who stop oral antibiotic therapy or decrease the dose of concomitant oral antibiotic therapy during the Screening Period will still be randomized and will continue to receive IMP if they stop oral antibiotic therapy or decrease dose of concomitant oral antibiotic therapy during the Treatment Period (refer to [Table 7](#)).

**Table 7 - Antibiotic therapy**

| Antibiotic                                  | Indication                    | Study Period                     | Increase Dose or Frequency of Antibiotic   | Decrease Dose or Frequency of Antibiotic  | Stop Antibiotic |
|--|--------------------------------------|---|---|--|------------------------|
| Permitted oral antibiotic*                  | HS                                   | Screening Period (after enrollment)     | See exclusion criteria.   | If this occurs, the Baseline Visit must be scheduled at least 2 weeks from date that change in medication administration was implemented by participant. |                        |
|  |                                      | Treatment Period (after Baseline Visit) | Prohibited.   | Permitted.   |                        |
|  |                                      | Follow-up Period (after EOT visit)      | Permitted without any dose restriction per Investigator discretion.   |  |                        |
| Systemic (oral or IV) or topical antibiotic | Non-HS (eg, urinary tract infection) | Screening Period (after enrollment)     | Permitted without any dose restriction per Investigator discretion. However, the Baseline Visit must be scheduled 14 days after the last dose of oral antibiotic was taken by the participant and 30 days after the last dose of IV antibiotic was taken by the participant (ie, participant may need to be re-screened). |  |                        |
|  |                                      | Treatment Period (after Baseline Visit) | Permitted without any dose restriction per Investigator discretion.   |  |                        |
|  |                                      | Follow-up Period (after EOT Visit)      | Permitted without any dose restriction per Investigator discretion.   |  |                        |

Abbreviations: EOT=end of treatment; HS=hidradenitis suppurativa; IV=intravenous; mg=milligram(s); PO=oral

\*Permitted oral antibiotics are stable doses of doxycycline up to 100 mg PO BID or minocycline up to 100 mg PO BID.

- Use of any treatments for HS-related pain including but not limited to antiepileptics (eg, gabapentin), tricyclics (eg, nortriptyline), or selective serotonin norepinephrine reuptake inhibitors (eg, duloxetine, venlafaxine). Use of any opioid is prohibited, regardless of the indication. Exception:
  - Ibuprofen (at a dose of up to 800 mg PO every 6 hours not to exceed 3.2 gm/24 hours) and/or acetaminophen (at a dose of up to 1000 mg PO every 6 hours not to exceed 4.0 gm/24 hours or a lower maximum dose as per local regulations) provided the dose is stable (PRN is not considered stable) 10 days before Baseline and continued until Week 28 for HS-related or HS-unrelated pain,
  - Ibuprofen (at a dose of up to 800 mg PO every 6 hours not to exceed 3.2 gm/24 hours) and/or acetaminophen (at a dose of up to 1000 mg PO every 6 hours not to exceed 4.0 gm/24 hours or a lower maximum dose as per local regulations) can be taken after Baseline Visit for HS-related or HS-unrelated pain,
  - Participants in Australia may receive tramadol (at a dose of up to 100 mg PO every 4 hours, not to exceed 400 mg/24 hours) as a rescue therapy after Baseline for HS-related pain that is refractory to treatment with ibuprofen or acetaminophen per Investigator discretion,

- Local anesthetic administered in the setting of rescue treatment with intralesional triamcinolone acetonide injection after Week 16 (Visit 10) provided the number of protocol-allowed interventions is not exceeded (Note: For participants in Australia, 2 lesion interventions are allowed during Period A prior to Week 16 [Visit 10]) (See [Section 6.9.2](#)),
- Local anesthetic administered in the setting of rescue treatment with local I&D after Week 16 (Visit 10) provided the number of protocol-allowed interventions is not exceeded (Note: For participants in Australia, 2 lesion interventions are allowed during Period A prior to Week 16 [Visit 10]) (See [Section 6.9.2](#)),
- Local anesthetic administered in the setting of [REDACTED]
- Non-opioid analgesics for HS-unrelated pain provided dose is stable for 14 days prior to Baseline and is continued until Week 28 for HS-unrelated pain.
  - Participants who receive prohibited analgesic therapy for HS-related pain or non-HS-related pain will continue to receive IMP (refer to [Table 8](#)).

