### 7.1 DISCONTINUATION OF STUDY INTERVENTION

#### 7.1.1 Permanent discontinuation

It may be necessary for a participant to permanently discontinue study intervention. If study intervention is permanently discontinued, the participant should, if at all possible, remain in the study to be evaluated for all assessments indicated in the SoA. See the SoA for data to be collected at the time of discontinuation of study intervention and follow-up and for any further evaluations that need to be completed.

Under the following circumstances IMP should be permanently discontinued:

- At participant's own request or at the request of their LAR (ie, an individual or judicial or other body authorized under applicable law to consent on behalf of a prospective participant to the participant's participation in the procedure(s) involved in the research).
- If, in the Investigator's opinion, continuation in the study would be detrimental to the participant's well-being.
- At the specific request of the Sponsor.
- In the event of a protocol deviation, at the discretion of the Investigator or the Sponsor.
- Severe allergic or hypersensitivity reaction (See [Section 10.6](#)).
- Confirmed diagnosis of malignancy.
- Major surgery or elective surgical procedure.
- Severe intercurrent illness.
- Pregnancy (See [Section 8.4.5](#)).
- Any opportunistic infection, such as TB or other infections whose nature or course may suggest an immunocompromised status (See [Section 10.6](#)).
- Severe laboratory abnormalities:
  - Neutrophil count  $<1\ 500/\text{mm}^3$  (See [Section 10.6](#)).
  - Platelet count  $<100\ 000/\text{mm}^3$  (See [Section 10.6](#)).
  - ALT  $>5\ \text{ULN}$  or ALT  $>3\ \text{ULN}$  with concomitant total bilirubin  $>2\ \text{ULN}$  (unless participant with documented Gilbert's syndrome) (See [Section 10.6](#)).
  - Increase in serum creatinine as per algorithm in [Section 10.6](#).
- Any clinically significant abnormal laboratory value will be immediately rechecked for confirmation after 24 hours before making a decision of permanent discontinuation of the IMP for the concerned participant. If the laboratory abnormality is considered causally related to the IMP, the IMP will be permanently discontinued. In cases where a causal

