relationship to the IMP can be reasonably excluded (ie, an alternative cause is evident), the IMP will be discontinued but it may be resumed when the laboratory abnormality is sufficiently normalized. A decision to resume the IMP will be made jointly by the Investigator and Medical Monitor (Medical Monitor's written approval is required).

- Occurrence of AEs, that, in the opinion of Investigator/Sponsor, may jeopardize participant's safety or data integrity.
- Initiation of systemic immunosuppressive or immunomodulating drugs such as those described in [Section 6.9.1](#).
- Receipt of a live (attenuated) immunization.
- Treatment with any prohibited systemic concomitant medication or procedure (See [Section 6.9.1](#)).
- Treatment with any prohibited rescue medication or procedure (See [Section 6.9.1](#)).
- Missing >2 doses of scheduled IMP administration.

See the SoA ([Section 1.3](#)) for data to be collected at the time of definitive intervention discontinuation and follow-up and for any further evaluations that need to be completed. Any abnormal laboratory value or ECG parameter will be immediately rechecked for confirmation after 24 hours before making a decision of permanent discontinuation of the IMP for the concerned participant.

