### **Handling of participants after permanent intervention discontinuation**

Participants will be followed-up according to the study procedures specified in this protocol up to the scheduled date of study completion, or up to recovery or stabilization of any AE to be followed-up as specified in this protocol, whichever comes last.

If possible, and after the permanent discontinuation of intervention, the participants will be assessed using the procedure normally planned for the last dosing day with the IMP including a pharmacokinetics sample, if appropriate.

All cases of permanent intervention discontinuation must be recorded by the Investigator in the appropriate pages of the eCRF when considered as confirmed.

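### Protocol 6.9.1 keeps a participant who takes a prohibited analgesic on IMP while 7.1.1 stops them; separately, SoA footnotes d and e schedule no Week 16 lesion count after an early Period A stop

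*Protocol*

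**What the plan says.** **Prohibited analgesics.** Protocol 6.9.1 sets the consequence by drug class. For opioids it says "Use of any opioid is prohibited, regardless of the indication", with a tramadol allowance for Australia, and then "Participants who receive prohibited analgesic therapy for HS-related pain or non-HS-related pain will continue to receive IMP". For antibiotics it does the opposite: participants "meet criteria for permanent discontinuation if they start oral antibiotic therapy" or increase its dose for HS during treatment.

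Protocol 7.1.1 opens its list with "Under the following circumstances IMP should be permanently discontinued". Two bullets matter here: "Treatment with any prohibited systemic concomitant medication or procedure" and "Treatment with any prohibited rescue medication or procedure". Each points to 6.9.1, and neither mentions analgesics.

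**Assessment after a stop.** Protocol 7.1.1 says "the participant should, if at all possible, remain in the study to be evaluated for all assessments indicated in the SoA". Its paragraph on handling after a permanent stop adds "Participants will be followed-up according to the study procedures specified in this protocol up to the scheduled date of study completion". SoA footnote d (1.3.1) and footnote e (1.3.2, US) describe a shorter path: an EOT visit as soon as possible, resumption of HS treatment if needed, and an EOS visit eight weeks later. In both schedules the HS Clinical Parameters row is marked at EOT and blank at EOS.

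**Analysis.** Protocol 9.2.2.2 and SAP 2.2.2 apply treatment policy to stops for reasons other than lack of efficacy, and the composite strategy to stops for lack of efficacy and to starting or increasing oral antibiotics. SAP Table 13 opens the Week 16 lesion-count window on Day 99. SAP 4.4 treats a visit with no measurement in its window as missing, and SAP 2.2.2 scores missing HiSCR50 as non-response.

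**The concern.** The first conflict concerns dosing. A site that works from the 7.1.1 list stops IMP after a single opioid prescription, and a site that works from 6.9.1 continues. The same event then leads to different treatment at different sites, and some participants lose study drug that 6.9.1 says they should receive.

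The second concerns the primary endpoint. A treatment-policy estimand needs the Week 16 count from participants who have stopped. If the schedule does not provide that count, the missing-data rule supplies non-response, and a participant whose lesions had responded can be recorded as a failure.

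The two can meet. If a site stops IMP for an opioid under 7.1.1 and follows the footnote path, an event that the SAP does not count as HiSCR50 failure can end as one through missing data.

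**Working it through.** **Part 1: the two rules side by side**

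| Event in the Treatment Period | 6.9.1 | 7.1.1 | Agree? |
|---|---|---|---|
| Oral antibiotic for HS started or increased | Permanent stop | Permanent stop | Yes |
| Systemic opioid outside the Australian allowance | IMP continues | Permanent stop | No |

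The systemic-medication bullet is the clear collision. The rescue bullet fits less well: in 6.9.1 and 6.9.2 the word rescue describes intralesional steroid, incision and drainage, and the permitted Australian tramadol. Other opioids and gabapentin are not called rescue.

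SAP Table 5 lists analgesics only under the pain endpoints. For HiSCR50 they therefore count as other prohibited medications, handled by treatment policy. That agrees with 6.9.1.

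**Part 2: the visit path after a Period A stop**

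Inputs: visit days from the SoA, EOS = EOT + 8 weeks from footnotes d and e, and the Day 99 opening from SAP Table 13.

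| EOT visit | Day | In Week 16 window? | EOS falls at | Lesion count at EOS? |
|---|---|---|---|---|
| Week 2 | 15 | No | Week 10 | No |
| Week 4 | 29 | No | Week 12 | No |
| Week 6 | 43 | No | Week 14 | No |
| Week 8 | 57 | No | Week 16 | No |
| Week 10 | 71 | No | Week 18 | No |
| Week 12 | 85 | No | Week 20 | No |
| Week 14 | 99 | Yes | Week 22 | Not needed |

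For six visits the footnote path contains no lesion count on or after Day 99. With EOT at Week 8 the participant attends in Week 16 for EOS, yet no count is scheduled.

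**Part 3: what one lost count does**

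Inputs: 66 naïve participants at 2:1 give 44 active and 22 placebo. The placebo prior is Beta(2.1, 4.9) (SAP 2.2.2), with mean 2.1/7 = 30% and weight 2.1 + 4.9 = 7.

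The plan's own precision figure (Protocol 9.5) is an 80% half-width below 0.145. The rates in Table 10 are redacted, so observed rates are assumed. With placebo at 30%, active at 40% to 70%, a Beta(1, 1) active prior and no Hurley term, the half-width is 0.138 to 0.143, in line with the plan. With placebo at 35% it reaches 0.146 at worst. That figure is not in dispute and serves only as a yardstick.

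Per responder recorded as a non-responder:

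- active rate: 1/44 = 2.3 points;
- placebo raw rate: 1/22 = 4.5 points;
- placebo posterior mean: 1/(22 + 7) = 1/29 = 3.4 points.

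The SAP logistic model with its Hurley term gives much the same. Assuming an equal Hurley split and 7/22 placebo responders, losing one moves the placebo posterior mean from 31.08% to 27.66% (3.4 points). Losing one of 26/44 active responders moves the active mean from 59.32% to 56.95% (2.4 points).

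Shift in the posterior difference = -100 × a/44 + 100 × p/29, for a lost active and p lost placebo responders. Illustrative counts:

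- a = 2, p = 0: -4.5 points;
- a = 1, p = 1: +1.2 points;
- a = 0, p = 2: +6.9 points.

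The sign depends on which arm loses responders. The documents give no stop rate from which to predict it.

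**The case against.** **On analgesics.** Both 7.1.1 bullets refer to 6.9.1, where a specific rule says to continue, and a specific rule normally governs a general one. 6.9.1 also tells investigators to take questions to the Medical Monitor. This stands as evidence of intent. It does not remove the conflict: 6.9.1 is also where the prohibited drugs are listed, so the cross-reference can be read as naming the drugs that trigger a stop. Prohibited use may also be uncommon, since E 19 excludes opioid use within 14 days before Baseline and ibuprofen and acetaminophen are allowed afterwards.

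**On the Week 16 count.** The protocol is not silent. 7.1.1 asks for all SoA assessments, 7.2 asks investigators to discuss key visits with participants who no longer wish to take IMP, and SAP 4.4 accepts unscheduled efficacy measurements that fall in a window. The footnotes do not expressly cancel Week 16. All of this stands, and it means a careful site can obtain the count. But 7.1.1 sends the reader to the SoA for what to collect after a stop, and the SoA gives the shorter path.

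**On who is affected.** A reader might infer that every early stopper who responded is misclassified. The documents do not support that. Stops for lack of efficacy are non-response by definition. The footnotes let participants resume HS treatment at EOT, including oral antibiotics, and starting these for HS before Week 16 is also non-response by definition. For both groups an extra count changes nothing.

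**Conclusion.** Both inconsistencies are real, and both are minor.

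1. 6.9.1 and the systemic-medication bullet of 7.1.1 order opposite actions for the same event. The likely intent is to continue IMP. A reader might infer that opioid users will be counted as HiSCR50 failures. The SAP does not say so: while IMP continues, analgesic use is a treatment-policy event for that endpoint.

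2. For Period A stops with EOT before Day 99, footnotes d and e conflict with 7.1.1 and omit a count that the treatment-policy estimand needs. The gap is confined to participants who stop for reasons other than lack of efficacy and have no other composite event before Week 16. A reader might also infer a biased treatment difference. None is shown: the number affected is not in the documents, the counts used above are assumptions, and the shift can go either way. The supportable statement is one of sensitivity: a single lost responder is worth about 2.3 points on active or 3.4 points in the placebo posterior mean, against a planned 80% half-width below 14.5 points.

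**What to change.** **7.1.1.** Add to the prohibited systemic medication bullet: *except prohibited analgesics, for which IMP continues (see 6.9.1)*. Adding the same words to the rescue bullet is optional.

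**Footnotes d (1.3.1) and e (1.3.2).** Add: *Participants who stop IMP in Period A still have HS Clinical Parameters at the scheduled Week 16 date (Day 113, or at least within the SAP Table 13 window from Day 99). The EOS visit takes place 8 weeks after EOT or at the Week 16 date, whichever is later.* The second sentence is needed because EOT at Week 2, 4 or 6 otherwise puts EOS at Week 10, 12 or 14, before the Week 16 count.

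**Cost.** A protocol wording amendment, with the ethics approval that Protocol 10.1.1 requires before implementation, a note to sites, and one lesion count per affected participant that 7.1.1 already asks for. For the earliest stoppers, EOS also moves to the Week 16 date. No change to the design, sample size or model is needed.

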**Table 8 - Analgesic therapy**

| Analgesic  | Indication | Study Period                     | Increase Dose or Frequency of Analgesic  | Decrease Dose or Frequency of Analgesic | Stop Analgesic |
|---|-------------------|---|---|--|-----------------------|
| Opioid Analgesics  | HS or non-HS      | Screening Period (after enrollment)     | See exclusion criteria.   |  |                       |
|   |                   | Treatment Period (after Baseline Visit) | Prohibited for all participants except for participants in Australia.†                                      |  |                       |
|   |                   | Follow-up Period (after EOT Visit)      | Permitted per Investigator discretion.  |  |                       |
| Non-opioid Analgesics (eg, gabapentin) Excluding Ibuprofen and Acetaminophen | Non-HS            | Screening Period (after enrollment)     | Stable doses of non-opioid analgesics are permitted.  |  |                       |
|   |                   | Treatment Period (after Baseline Visit) | Prohibited. Dose must remain stable.  |  |                       |
|   |                   | Follow-up Period (after EOT Visit)      | Permitted per Investigator discretion.  |  |                       |
| Non-opioid Analgesics (eg, gabapentin) Excluding Ibuprofen and Acetaminophen | HS                | Screening Period (after enrollment)     | Non-opioid analgesics are prohibited.   |  |                       |
|   |                   | Treatment Period (after Baseline Visit) |   |  |                       |
|   |                   | Follow-up Period (after EOT Visit)      | Permitted per Investigator discretion.  |  |                       |
| Ibuprofen  | HS or non-HS      | Screening Period (after enrollment)     | Stable doses of ibuprofen are permitted.  |  |                       |
|   |                   | Treatment Period (after Baseline Visit) | If medically necessary, permitted per Investigator discretion provided dose does not exceed maximum limit.* |  |                       |
|   |                   | Follow-up Period (after EOT Visit)      | Permitted without any dose restriction per Investigator discretion.   |  |                       |

| Analgesic               | Indication  | Study Period                            | Increase Dose or Frequency of Analgesic  | Decrease Dose or Frequency of Analgesic | Stop Analgesic |
|-------------------------|---|---|--|---|----------------|
| Acetaminophen    | HS or non-HS

[REDACTED]
for biomarker assessment      | Screening Period (after enrollment)     | Stable doses of acetaminophen are permitted.   |   |                |
|                         |   | Treatment Period (after Baseline Visit) | If medically necessary, permitted per Investigator discretion provided dose does not exceed maximum limit.**   |   |                |
|                         |   | Follow-up Period (after EOT Visit)      | Permitted without any dose restriction per Investigator discretion.  |   |                |
| Local Anesthetic | Prior to [REDACTED]
for biomarker assessment                 | Screening Period (after enrollment)     | Permitted without any dose restriction per Investigator discretion.  |   |                |
|                         |   | Treatment Period (after Baseline Visit) |  |   |                |
|                         |   | Follow-up Period (after EOT Visit)      |  |   |                |
| Local Anesthetic | Prior to intralesional triamcinolone injection or in-office I&D | Screening Period (after enrollment)     | See exclusion criteria.  |   |                |
|                         |   | Treatment Period (after Baseline Visit) | Prohibited until after completion of Week 16 (Visit 10). After Week 16, permitted, provided that participant maximally has two interventions every 4 weeks.§ |   |                |
|                         |   | Follow-up Period (after EOT Visit)      | Permitted without any dose restriction per Investigator discretion.  |   |                |

Abbreviations: EOT=end of treatment; HS=hidradenitis suppurativa; I&D=incision and drainage

¥ Participants in Australia may receive tramadol (at a dose of up to 100 mg PO every 4 hours, not to exceed 400 mg/24 hours) as a rescue therapy after Baseline for HS-related pain that is refractory to treatment with ibuprofen or acetaminophen per Investigator discretion.

§ For participants in Australia, 2 lesion interventions are allowed during Period A. An intervention can occur on two different lesions at the same visit or on the same lesion at two different study visits (See [Section 6.9.2](#)).

\* Maximum limit for ibuprofen is up to 800 mg PO every 6 hours not to exceed 3.2 gm/24 hours.

\*\* Maximum limit for acetaminophen is up to 1000 mg PO every 6 hours not to exceed 4.0 gm/24 hours or a lower maximum dose as per local regulations.

- Injectable corticosteroids. Exception: rescue treatment (intralesional triamcinolone acetonide via intradermal injection) after Week 16 (Visit 10).
- Deroofing or skin-tissue-saving excision with electrosurgical peeling, laser therapy, intense pulse light, local/wide/radical excision, incision and/or draining of lesions is prohibited. Exception: Rescue treatment (local I&D).
- Phototherapy treatment (ultraviolet B [UVB] or ultraviolet A [UVA] phototherapy, including psoralen and ultraviolet A), tanning booth, or extended sun exposure.
- Non-antibiotic topical therapies or changes in the concentration/frequency of such treatments that may be used to treat HS (eg, zinc pyrithione, resorcinol, dapsone, and delgocitinib). Other non-antibiotic topical treatments (eg, corticosteroids, antifungals, etc) are permitted, provided these are not being used in anatomic regions where HS lesions are located.
- Over-the-counter topical antiseptic washes, creams, ointments, gels, and liquids containing antibacterial agents to treat HS, other than those allowed as per concomitant therapy section.

- Live vaccines (during the study and for 6 months after the last dose of study drug). Examples of live attenuated vaccine include, but are not limited to, BCG vaccine, live zoster vaccine (Zostavax®), measles-mumps-rubella or measles-mumps-rubella-varicella vaccine, monovalent live attenuated influenza A (intranasal) vaccine, oral polio vaccine, rotavirus vaccine, seasonal trivalent live attenuated influenza (intranasal) vaccine, smallpox vaccine, oral typhoid vaccine, varicella (chicken pox) vaccine, yellow fever vaccine, or dengue fever vaccine (Dengvaxia®).
- Natalizumab (Tysabri®).
- Rituximab.
- Any investigational agents.
- Medicinal and recreational cannabis or cannabinoid use.
- Herbal medications for HS or non-HS indications.

The Investigator should contact the Medical Monitor if there are any questions regarding concomitant or prior therapy.

In addition, any medications listed in exclusion criteria (from [E 16](#) to [E 24](#)) should not be initiated during the study except what is specifically mentioned in the concomitant-medication section.

During Period C, the safety Follow-up Period, these medications may be resumed per the discretion of the Investigator.

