### **Lesion Intervention**

In the event that an acutely painful lesion occurs that requires an immediate intervention, Investigators will have the option to perform protocol-allowed interventions.

Only 2 types of interventions are allowed: injection with intralesional triamcinolone acetonide suspension (at a concentration of up to 10 mg/mL, up to 1 mL) and I&D.

For participants in Chile, intralesional betamethasone (at a maximum dose of up to 1.5 mg, diluted in sterile normal saline per Investigator discretion) may be substituted for intralesional triamcinolone.

New systemic and topical therapies following I&D (including antibiotics), are prohibited.

Participants should continue using any ongoing oral and topical therapies (with the constraints as described in [Section 6.9.1](#)) during the study. Concomitant medications associated with the lesion intervention(s) must be captured in the source and on the appropriate eCRF.

Protocol-allowed interventions are prohibited during Period A for all participants except those in Australia. For participants in Australia, 2 lesion interventions are allowed during Period A. An intervention can occur on two different lesions at the same visit or on the same lesion at two different study visits.

During Period B, maximally two interventions every 4 weeks are permitted. An intervention can occur on two different lesions at the same visit or on the same lesion at two different study visits.

All study visit assessments must occur before any interventions are performed. The site will be required to count any lesion that undergoes an intervention as permanently present from the date of the intervention and must account for it in the source document(s) and on the appropriate eCRF.

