### **10.8.3 Australia**

Participants in Australia may receive tramadol (at a dose of up to 100 mg PO every 4 hours, not to exceed 400 mg/24 hours) as a rescue therapy after Baseline for HS-related pain that is refractory to treatment with ibuprofen or acetaminophen per Investigator discretion.

Participants in Australia are permitted two lesion interventions during Period A. An intervention can occur on maximally two different lesions at the same visit or on the same lesion at two different study visits. The same lesion cannot be treated two times at the same visit. Please refer to [Section 6.9.2](#).

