### **10.8.4 Chile**

For participants in Chile, intralesional betamethasone (at a maximum dose of up to 1.5 mg, diluted in sterile normal saline per Investigator discretion) may be substituted for intralesional triamcinolone.

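### Two bullets in protocol Section 6.9.1 do not match the lesion-rescue rule in 6.9.2 and the country appendices, so a permitted steroid injection is literally a permanent-stop event and the status of early drainage is unclear

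*Protocol*

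**What the plan says.** Two bullets of Section 6.9.1, placed after Table 8, deal with rescue of a painful lesion.

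- Steroid bullet: "Injectable corticosteroids. Exception: rescue treatment (intralesional triamcinolone acetonide via intradermal injection) after Week 16 (Visit 10". It names one drug and one period, and no country.
- Drainage bullet: "incision and/or draining of lesions is prohibited. Exception: Rescue treatment (local I&D". It gives neither a period nor a country.

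Section 6.9.2, under Lesion Intervention, sets out the fuller rule. It covers triamcinolone injection and incision and drainage (I&D): "Only 2 types of interventions are allowed: injection with intralesional triamcinolone acetonide suspension", with I&D as the second type. On timing it says "Protocol-allowed interventions are prohibited during Period A for all participants except those in Australia", followed by "For participants in Australia, 2 lesion interventions are allowed during Period A". In Period B it caps interventions at two every 4 weeks. For Chile it lets betamethasone replace triamcinolone.

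The country appendices agree with 6.9.2. Section 10.8.3 says "Participants in Australia are permitted two lesion interventions during Period A". Section 10.8.4 says that betamethasone "may be substituted for intralesional triamcinolone".

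Section 7.1.1 lists, among the reasons for permanent discontinuation of IMP, "Treatment with any prohibited rescue medication or procedure", and refers the reader to Section 6.9.1 for what is prohibited.

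**The concern.** A site that wants to know whether it may inject or drain a lesion gets different answers from different parts of the protocol, and the stop rule points to the section whose bullets are out of line. The same act could be recorded as permitted rescue with IMP continued, or as prohibited rescue with IMP permanently stopped.

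What is at stake is consistency between sites in three things: who is taken off treatment, what is logged as a protocol deviation, and whether a Week 16 lesion count exists. Demand for rescue in Period A is foreseeable. Section 4.2.1 reports that the patient panels found 16 weeks on placebo too long if no rescue was available.

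**Working it through.** No arithmetic applies, so the texts are set side by side.

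| Case | 6.9.1 bullet | 6.9.2 and appendix | Result |
|---|---|---|---|
| Triamcinolone, Australia, Period A | Prohibited (exception starts after Week 16) | Permitted, up to two (6.9.2, 10.8.3) | Conflict; a stop event on a literal reading of 7.1.1 |
| Betamethasone, Chile, Period B | Prohibited (only triamcinolone is excepted) | Permitted as a substitute (6.9.2, 10.8.4) | Conflict; a stop event on a literal reading of 7.1.1 |
| I&D outside Australia, Period A | Excepted | Prohibited (6.9.2) | Conflict; stop status unclear |
| I&D, Australia, Period A | Excepted | Permitted, up to two | No conflict on permission; only 6.9.2 and 10.8.3 cap the number |
| Triamcinolone outside Australia, Period A | Prohibited | Prohibited | No conflict |

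**Precedence.** Section 6.9.2 opens by permitting treatments apart from those that 6.9.1 prohibits, so where the two differ 6.9.1 appears to govern. The stop criterion in 7.1.1 also cites 6.9.1. This makes the first two rows literal stop events.

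**Drainage outside Australia.** The bar is in 6.9.2, which the 7.1.1 rescue criterion does not cite, and the bullet in 6.9.1 excepts the procedure. Section 7.1.1 separately allows a stop for a protocol deviation at the discretion of the investigator or sponsor. A stop is therefore possible but not clearly required.

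**The rest of 6.9.1.** Its local-anesthetic exceptions place both rescue triamcinolone and rescue I&D after Week 16, note the two Australian interventions in Period A, and refer to 6.9.2. The local-anesthetic row of Table 8 repeats the Week 16 limit with an Australian footnote. These lines govern the anesthetic, not the procedure. They still carry the 6.9.2 rule inside 6.9.1, so the section disagrees with itself.

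**Route to the primary endpoint.**

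1. Lesions that receive an intervention stay counted as present (protocol 6.9.2; SAP 2.1).
2. For HiSCR50, SAP Table 5 gives intralesional corticosteroids treatment-policy handling. It lists I&D only under the pain endpoints. A separate row, for corticosteroids with systemic potential, is handled as non-response if blinded review confirms it.
3. Stopping IMP for a reason other than lack of efficacy is also treatment policy (SAP 2.2.2).
4. The remaining route is a missing count. Footnote d of the schedule in 1.3.1 sends early stoppers to an end-of-treatment visit as soon as possible and then to an end-of-study visit 8 weeks later. Lesions are counted at the first of these visits but not at the second. The Week 16 window opens at Day 99 (SAP Table 13). A participant who stops earlier and attends only those two visits has no Week 16 count and is imputed as a non-responder.

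Only Period A events can act this way. The Chilean conflict arises in Period B and cannot affect Week 16.

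**The case against.** The strongest reply is that a site reading the whole protocol would reach the right answer. The drainage exception is silent on timing rather than contrary to 6.9.2. The anesthetic lines and Table 8, both in 6.9.1, give the Week 16 limit and the Australian allowance. The country appendices are specific provisions, and the Chilean text is a plain substitution clause. Section 6.9.1 also tells investigators to raise questions with the Medical Monitor.

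Much of this stands. A reader might infer that Section 6.9.1 as a whole leaves drainage without a time limit and bans early injections everywhere. That is true of the two bullets but not of the section.

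It does not remove the conflict. The anesthetic lines do not regulate the procedure. The steroid bullet is explicit, not silent, and it contradicts the Australian and Chilean permissions. Section 6.9.1 does defer to the concomitant-medication section, but only for treatments listed in exclusion criteria E 16 to E 24. Nothing states that the appendices override the bullets for the purpose of 7.1.1.

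The second reply is that the primary endpoint is protected. This is largely right. Treated lesions remain counted, and 7.1.1 asks participants who stop IMP to stay for all scheduled assessments if at all possible. That reduces the missing-count route but does not close it.

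**Conclusion.** Wrong as written. The steroid bullet contradicts 6.9.2, 10.8.3 and 10.8.4, and through 7.1.1 it turns permitted injections into literal grounds for permanent discontinuation. The drainage bullet does not match 6.9.2 or the rest of 6.9.1, and whether an early drainage outside Australia is a stop event cannot be settled from the text.

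The direct effect is on IMP stopping and on deviation classification. The effect on HiSCR50 is indirect and conditional: it needs a Period A stop followed by no lesion count in the Week 16 window.

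Two stronger readings are not supported:

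- A reader might infer that rescue itself makes a participant a HiSCR50 non-responder. SAP Table 5 does not say so for ordinary intralesional steroid or for I&D.
- A reader might try to size the problem from the share of participants eligible for early rescue under each reading. The documents do not give the Australian share of enrolment. Australia is one of 15 countries named in SAP Appendix 3, which says nothing about numbers enrolled. Eligibility is also not use, discontinuation or a changed response.

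No numerical magnitude can be given.

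**What to change.** Reconcile the two 6.9.1 bullets, the local-anesthetic exceptions and Table 8 in 6.9.1, the Lesion Intervention text in 6.9.2, and Sections 10.8.3 and 10.8.4. State one period and country rule for I&D and one for intralesional steroid, including which steroid is meant in which country, and use identical wording in every place. Add to 7.1.1 that an intervention permitted under that rule is not a prohibited rescue medication or procedure, and say whether one that falls outside it requires a stop. Which rule applies is for the sponsor to decide; none is proposed here.

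The cost is protocol wording in a few places and a clarification letter to sites. No participants, visits or procedures are added.
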